At the time of writing, it is unclear what volume of patients have been referred to the CO@h pathway, and what onboarding data will be available due to pressure on the system to cope with the pandemic. As a result, the study may be underpowered. This risk is further exacerbated by the fact that the primary outcomes relate to use of critical care beds and mortality. The mixed-methods study of pilots of remote home monitoring models in England

found that for the pre-hospital model of CO@h, although 10% (174/1,737) of patients that were monitored deteriorated and were escalated, 0.2% (3/1,737) of patients were admitted to ICU and 1% (20/1,737) died.¹ See the Power calculation section for further details

All decisions taken after this statistical analysis protocol (SAP) has been finalised will be documented and justified in an addendum to it. We may run interim analyses on incomplete data to provide the CO@h programme team with some preliminary indications of results. The results of the final analysis will be published in line with the Health Foundation's Improvement Analytic Unit's (IAU's) aim of openness and transparency.

Study outcomes

We will analyse outcomes in the 28-day period following a COVID-19 positive test (ie equal to or less than 28 days from a positive test, with the date of the first COVID-positive test being equal to day zero). We are limiting most of the outcomes to binary variables (ie capturing whether there was an A&E attendance rather than the number of attendances); this is because of the short follow-up period and likely sparsity in hospital event counts other than 0 and 1 (which we will confirm on receipt of the data). The following outcomes will be included:

- Type 1 A&E attendance (binary outcome yes/no)
- Emergency admission (binary outcome yes/no)
- Critical care bed use (binary outcome yes/no)
 - This will capture a stay in ICU at any point during an admission, which could be as a result of either an emergency or an elective admission.
 - This variable includes level 2 and level 3 beds, as well as beds under code 5 (flexible critical care beds where there is a mix of level 2 and level 3 beds) and code 90 (temporary use of non-critical care beds).¹²
- Total emergency hospital bed days

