 - This includes all hospital bed days during emergency admissions in the 28 days from first COVID-19 positive test. If the patient is still in hospital on day 28 then bed days will be truncated on day 28. Except for same-day admissions, bed days are counted as number of nights in hospital. Thus, an admission on day one and discharge on day three would equate to two bed days. Same day admission-discharges will be treated as a half-day.
 - We will evaluate total hospital bed days as opposed to average length of stay (LOS) in order to better capture the hospital resources required to care for a patient. For example, a patient's single stay of 3 days or two stays of 3 days would both result in an average LOS of 3 days, whereas the total number of hospital bed days would be 3 and 6 days, respectively.

- Total hospital bed days in critical care
 - This includes all bed days in critical care (see definition above) in the 28 days from first COVID-positive test. If the patient is still in a critical care bed on day 28 then bed days will be truncated on day 28. Same-day admission-discharges will be treated as a half-day.
- Death (binary yes/no)
 - This will include deaths recorded within the 28-day follow-up period. This is consistent with the definition of COVID-19 deaths used for reporting by Public Health England.

Hypothesised outcomes

The primary outcomes for this study are whether a patient was allocated a critical care bed, total hospital bed days in critical care, and death. The CO@h programme's logic model hypothesises that early escalation of deteriorating patients will result in fewer patients needing critical care, less time spent in critical care, and fewer deaths. It may be, however, that a decrease in mortality results in longer stays in hospital, on average, due to more patients surviving while still becoming severely ill.

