4. **Check that CEV and care home patients should be excluded.** We will also check for an age-related discontinuity in onboarding of CEV and care home residents and exclude these patients from the analysis if there is no discontinuity to exploit at age 65:
 - CEV (yes/no)
 - Care home residents (yes/no)

Window selection

Although we expect there to be a trend in the proportion of patients with certain characteristics by age (eg multimorbidity, diabetes), the local randomisation approach assumes there is a window around the threshold where there are no statistically significant differences between treated and control patients. The symmetric window around the threshold that we will use in our analysis will be identified through a data-driven approach formulated by Cattaneo et al.¹⁷ The baseline variables will be exploited to identify the largest window around the age 65 threshold within which there is no evidence that the patients vary significantly between groups in terms of those baseline variables. By identifying this window, an age range is identified across which the groups of patients can be said to be comparable at baseline. These patients are then used in the main analysis to estimate treatment effects. This method assumes that the baseline variables adequately account for differences in pre-intervention characteristics within this window that might affect outcomes and vary by age. This assumption implies that the outcomes are conditionally independent of the baseline variables.

The window will be identified by first conducting tests of mean differences in the baseline variables at the narrowest window – ie 1 week either side of the age 65 threshold, and with a minimum of 10 observations (patients) per group. Each baseline variable will be tested and the smallest resulting p-value reported. The window will then be increased by 1 week either side of the threshold and the process repeated. The maximum window used in the main analysis will be the smaller of (a) the one immediately prior to the window where a statistically significant

difference between groups is first identified, or (b) the one where the sample size achieved should comfortably identify a statistically significant difference in the outcome based on power calculations*.

Although we believe that the window will be determined by (a), the criterion in (b) will ensure that any potential for unobserved confounding caused by the use of a very wide window is limited.

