The null hypothesis for the Fisher-based simulation will assume complete randomisation of patients to treatment within the window. A confidence interval will be estimated for the treatment effect by inverting the calculation for the Fisher-based p-value and identifying values of treatment effect which are not significantly different to the estimated effect. As a comparison to the Fisher-based approach, we will also estimate the p-value using the large-sample Neyman approach based on normal approximation, and also report the power of the Neyman test to inform interpretation.¹⁷ If the results of the Fisher and Neyman approaches differ, we will consider the number of observations within the window to determine which approach is most valid, with the Fisher framework being preferred where sample sizes within the window are small.

Many of our outcomes are binary. In these cases, the estimated treatment effects will comprise differences in mean outcomes on the per cent scale. For our other outcomes, the treatment effects will be differences in mean bed days. As well as the treatment effects, we will also present the point estimates for the treated and control groups in each case. We will not control for the baseline variables in the model, as the window selection procedure will already have been used to identify groups which are comparable in terms of these variables.

Calculation of intervention estimates where outcomes happen before enrolment

This evaluation aims to estimate the effect of pre-hospitalisation CO@h, as detailed in the SOP.² Although we will exclude any CCGs which are identified as only offering enrolment in CO@h at hospital discharge, it is conceivable that other CCGs may offer a combination of pre-hospital and post-discharge as part of the CO@h model, especially in those areas that had implemented a post-discharge model early on in the pandemic. There may therefore be some patients enrolled in CO@h at hospital discharge that we can identify by triangulating date of onboarding with date of hospital discharge. These patients will be considered as not having received the CO@h intervention (ie treatment receipt = 0), similar to those patients enrolled in CVWs (for whom we do not have data).

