1. Intention-to-treat analysis – we will use a sharp design (without taking account of compliance/oximeter receipt) to estimate the average effect of intervention eligibility at age 65, ie an intention-to-treat analysis.
2. Placebo outcomes – we will undertake statistical tests for treatment effects for each of the baseline variables and plot the means for each group, weekly averages and fitted constants to identify any evidence of infringement of the assumption of comparability of the groups.
3. Test of treatment assignment – we will use a binomial test to check that, within the specified window, treatment can be considered randomly assigned.
4. Influence of window choice – we will test a selection of windows smaller than the one used in the main analysis (minimum 10 patients either side of the threshold). We will not use larger windows as this may lead to biased estimates due to imbalances in baseline variables.¹⁷ By using smaller windows, this problem is avoided while also identifying whether restriction of the cohort to those increasingly closer to the threshold affects the treatment effect estimates. We will plot the resulting point estimates and confidence intervals.
5. Placebo thresholds – we will estimate treatment effects at both a lower and a higher threshold than age 65 to check that these spurious, placebo thresholds result in a treatment effect of zero. For these checks, we will only use control and treated patients,

respectively.¹⁷ We will test at thresholds centred on the first mass point past the end boundaries of the window used in the main analysis. We will use the same window size (ie number of mass points either side) as in the main analysis.¹⁷

6. Placebo study period – we will use data for a period before CO@h was implemented (ie in CCGs before they implemented CO@h) to check that there is no discontinuity in outcomes in a window around age 65 when no treatment was available. This will be a sharp RDD (as there will, by definition, be no intervention available). This sensitivity analysis will only be conducted if the intention-to-treat analysis using a sharp RDD (sensitivity analysis #1) is statistically significant.
7. Sensitivity to unmeasured confounding – we will calculate Rosenbaum’s sensitivity bounds, within the context of a local randomisation RDD, to estimate how large an unobserved confounder would need to be to affect the conclusions of the study.^{19,27}

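### Sensitivity analysis 4 sets its smallest window by patients (10 per side), not events, so narrow windows can hold no critical care stay or death and show an interval that says nothing about the effect

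*SAP*

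**What the plan says.** Item 4 of the SAP's Sensitivity analyses reruns the analysis in narrower windows and sets a floor for them: "we will test a selection of windows smaller than the one used in the main analysis (minimum 10 patients either side of the threshold"). Its purpose is "identifying whether restriction of the cohort to those increasingly closer to the threshold affects the treatment effect estimates", and the display is fixed: "We will plot the resulting point estimates and confidence intervals".

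The introduction to that section applies the checks to every primary outcome whatever the main result, and carries over the main design choices, including the fuzzy design, unless an item says otherwise. The primary outcomes (Hypothesised outcomes) are whether a patient was "allocated a critical care bed, total hospital bed days in critical care, and death".

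Under Main analysis, the interval comes from inverting the Fisher randomisation test, that is, by "identifying values of treatment effect which are not significantly different to the estimated effect". A Neyman p-value is reported alongside, and Fisher is preferred in small windows.

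The only ICU and death rates in the SAP are from the pilots: "0.2% (3/1,737) of patients were admitted to ICU and 1% (20/1,737) died" (Study design, repeated under Power calculation). The SAP sets no minimum number of events for a window and no rule for a window without events.

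**The concern.** The plot is meant to show whether the effect holds as the cohort is drawn closer to age 65. With a rare binary outcome, what a window can say depends on how many events it holds, and 10 patients per side guarantees none. An event-free window gives a point estimate of zero, and the interval around it does not widen to reflect the missing information in the way a reader expects.

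If the interval shrinks to a point, a genuine effect in the main window could look as if it disappears near the threshold, which would suggest confounding. A null main result could look confirmed with great precision. Either impression would come only from the absence of events, on a check meant to support the primary results.

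**Working it through.** **Inputs from the SAP.** Floor of 10 per side (Sensitivity analyses, item 4). Pilot risks 3/1,737 = 0.17% for ICU and 20/1,737 = 1.15% for death (Study design). Fisher inversion (Main analysis). Fuzzy design inherited (Sensitivity analyses). Expected main window about 5 years, or 260 weeks, either side (Study period, index dates and follow-up period). Uptake on each side of 65 is not given and is assumed below.

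**The plan's own figure.** Table 1 gives N = 21,590 for 2% v 1.5%. With pooled variance, n per group = [1.960 × √(2 × 0.0175 × 0.9825) + 0.842 × √(0.0196 + 0.014775)]² / 0.005² = 10,795, so N = 21,590. The table reproduces. It is used here only to gauge how many patients a week of age might hold.

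**Step 1: chance of no event in either group.** With n per side and common risk p, this is (1 − p)^(2n).

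| Patients per side | Critical care (0.17%) | Death (1.15%) |
|---|---|---|
| 10 | 97% | 79% |
| 20 | 93% | 63% |
| 42 | 86% | 38% |
| 50 | 84% | 31% |
| 100 | 71% | 10% |
| 200 | 50% | 1% |
| 500 | 18% | 0% |

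With no critical care stay, critical care bed days are all zero too, so those two primary outcomes fail together. With 10 per side, no events is the more likely result for any risk below 1 − 0.5^(1/20) = 3.4%.

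**Step 2: the interval in an event-free window.**

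- *Sharp design.* Testing an effect τ compares outcomes Y − τT, where T marks the side of 65. With Y = 0 for everyone, any τ other than 0 separates the groups completely. With 10 per side, p = 2/C(20,10) = 2/184,756 = 0.00001. Only τ = 0 is accepted, so the interval is the single point 0. The Neyman standard error is also 0.
- *Fuzzy design (Anderson-Rubin).* The test uses Y − τD, where D is enrolment. With Y = 0 this is −τD, so every τ other than 0 has the p-value of the permutation test of enrolment itself. If the uptake jump is significant in that window, the interval is the point 0; if not, it is the whole line. The ratio estimate is undefined if uptake is equal on both sides.

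**Step 3: which interval appears.** Exact probability of a significant uptake jump (two-sided 5%), by assumed uptake above v below 65:

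| Uptake | 10 per side | 42 | 50 | 100 | 200 |
|---|---|---|---|---|---|
| 70% v 10% | 67% | 100% | 100% | 100% | 100% |
| 35% v 5% | 16% | 94% | 97% | 100% | 100% |
| 10% v 2% | 0.1% | 13% | 19% | 59% | 92% |

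**Step 4: an event-free window with a zero-width interval.** Multiplying Steps 1 and 3 at 35% v 5%, taking uptake and events as independent:

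- Critical care: 15% with 10 per side, 81% with 42, 81% with 50, 71% with 100, 50% with 200.
- Death: 12% with 10 per side, 37% with 20 (where the jump is significant in 59%), 35% with 42, 30% with 50, 10% with 100.

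**Step 5: does the floor bind?** If the 5-year window held 21,590 patients spread evenly (an assumption), one week would hold 21,590/2/260 ≈ 42 per side. Step 1 then gives 86% and 38% event-free windows for critical care and death, with the 10-patient floor not reached.

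**The case against.** A reader might infer that windows at the floor will routinely show a precise zero, as though the effect vanishes at 65. The SAP does not support that, for four reasons.

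- Item 4 inherits the fuzzy design. At 35% v 5%, about 84% of event-free windows with 10 per side would show an unbounded interval, which nobody would take for precision. The SAP itself fears low compliance. For death at that uptake, the precise-zero picture is never the usual one at the sizes checked.
- Ten is a permitted minimum, not a planned size. Windows grow in whole weeks of age, and a multi-CCG cohort may hold well over 10 per side in a week.
- The rates come from onboarded pilot patients, and the ICU rate rests on 3 events. The cohort here is all test-positive, non-CEV patients near 65, and its critical care outcome also counts level 2, flexible and temporary beds. Above about 3.4% risk, event-free windows are no longer usual even at the floor.
- The main analysis presents estimates for each group and the power of the Neyman test. If item 4 is reported the same way, 0% v 0% would be visible. The SAP also warns repeatedly that primary events may be few.

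All four limit how often the misleading picture would occur. None supplies the missing rule. Moderate uptake moves the zero-width interval to somewhat larger windows, where critical care is still mostly event-free. If onboarding data are missing, the SAP falls back on the sharp design, where the interval in an event-free window is always the point 0. An interval that switches from the whole line to a point because enrolment became significant says nothing about the effect in either form.

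The same floor under Window selection ("with a minimum of 10 observations (patients) per group") governs baseline balance tests, where rare outcomes play no part, so it adds nothing here.

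**Conclusion.** The point holds in a limited form. A patient-based floor lets item 4 plot windows that hold no information on the primary outcomes, and the planned interval does not reveal this. At the cited pilot rates, windows at the floor are event-free in about 97% (critical care) and 79% (death) of cases. The harmful case, a zero-width interval, depends on uptake: at an assumed 35% v 5% it arises mainly for the two critical care outcomes with tens to a few hundred patients per side, and less often for death. At higher uptake it reaches down to the floor; at lower uptake it needs larger windows.

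The frequency is uncertain, because it rests on borrowed rates and assumed uptake. That the interval is uninformative in an event-free window does not depend on either. Main estimates, tests and intervals are unaffected. The change should be made because this check is meant to vouch for the primary results.

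**What to change.** In item 4, for each primary outcome:

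1. Print the number of events in each group under every window shown (for critical care bed days, the number of patients with any).
2. Mark a window with no events as not estimable, and do not plot a zero estimate and interval for it.
3. Replace the 10-patient floor by a pre-stated minimum number of events pooled over both groups. The pooled count ignores which side of 65 the events fell on, so the choice of windows does not follow the observed difference.

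The minimum is a judgement that the SAP should state in advance. At the pilot rates, each required event needs 1,737/(2 × 3) ≈ 290 patients per side for critical care and 1,737/(2 × 20) ≈ 43 for death.

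The cost is SAP wording only. The drawback is that few or no narrow windows may remain for critical care. The report should say so if it happens, since the check is then not available for those outcomes.

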2. Individuals 80 years of age or over and front-line health and social care workers
3. Individuals 75 years of age or over
4. Individuals 70 years of age or over and CEV individuals
5. Individuals 65 years of age or over
6. Individuals 16 years to 64 years of age with underlying health conditions which put them at higher risk of serious complications and mortality
7. Individuals 60 years of age or over
8. Individuals 55 years of age or over
9. Individuals 50 years of age or over

COVID virtual wards

COVID virtual wards (CVWs) is a national programme that aims for early supported discharge from hospital by providing additional support at home (including, but not limited to, pulse oximeters) to patients hospitalized due to COVID-19.⁶ CVWs is a complementary but separate programme to CO@h, predominately led from a hospital setting and targeting patients with higher acuity or complex conditions than the CO@h programme.

The CVWs programme was introduced at the end of December 2020 and is subsequently being rolled out across the country. It does not fall within the scope of the present evaluation.

PRINCIPLE trial

The PRINCIPLE trial is a national clinical trial to find effective COVID-19 drug treatments that can be taken at home; for example, one treatment included is a commonly used inhaled corticosteroid.⁷ The eligibility criteria are similar to CO@h: patients are enrolled if they are either symptomatic or testing positive for COVID-19 within the previous 14 days, are aged over 65, or aged over 50 and have certain underlying health conditions (which overlap but differ from the CEV list). Enrolment to PRINCIPLE started on 17 April 2020; as of 11 February 2021, 4,053 patients had been recruited to the trial.

Aim of the evaluation

The IAU will carry out two separate evaluations to quantify the impact of the roll-out of CO@h in England during the second wave of the COVID-19 pandemic on hospital activity and mortality. One evaluation will explore the impact of CO@h at the CCG level; the other is a patient-level analysis that will take advantage of the 65 years of age criterion for eligibility to estimate treatment effects. The latter evaluation is the subject of the remainder of this document.

Methods

Study design

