- **CO@h offboarding data** – these data will be used to check that our proposed 28-day follow-up period adequately captures the duration of CO@h use (which is intended to usually last up to 14 days from first symptoms, according to the SOP). The various quality issues affecting the onboarding data also affect this data set.
- **Hospital Episode Statistics (HES)** – this data set will include information on hospital admissions and critical care spells.

* Although we will estimate the intervention effect at age 65, we will require data on either side of the threshold to do so. The range or window of ages required will be determined using data-driven methods, but it is expected that 50–79 will be a large enough range not to restrict this choice prematurely.

- **Emergency Care Data Set (ECDS)** – this will be used to provide information on A&E attendances.
- **Office for National Statistics (ONS) mortality data** – this data set will include the registered date of death of any patients that died during the study period.
- **Data used to flag care home residents** – based on patient registration information derived from pseudonymised National Health Application and Infrastructure Services (NHAIS) data.

We will also receive information from Kent, Surrey & Sussex Academic Health Science Network (AHSN) on when each CCG began to implement CO@h and when they were considered ‘fully operational’ (see the later section on Study period, index dates and follow-up period). We will also access publicly available data that maps GP practices to CCGs at the earliest date of study start.

If onboarding data are delayed or unavailable, we may receive aggregate data on number of onboarded patients by CCG. This would allow us to determine whether areas are implementing CO@h at a scale sufficient to potentially identify an effect based on a ‘sharp’ RDD, whereby a treatment assignment effect is estimated (see later section on Statistical methods for more detail).

Study cohort

The study cohort consists of patients in England with a first COVID-19 positive test that were aged 50–79 at the time of test, with the following patient-level and area-level exclusions.

Patient-level exclusions:

- Patients with unlinked records
- Patients who are not captured in the GDPDR
- Patients with missing age or sex information
- Patients onboarded onto CO@h who do not have a first COVID-positive test
- Patients who are CEV
- Potential additional exclusion: patients living in care homes

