- Roll-out of vaccinations and other interventions (such as the PRINCIPLE trial, see Background section).
- The number of (documented) onboarded patients available for analysis.
- The requirements of the CO@h programme team to provide timely results across the evaluation programme.

We will monitor the vaccination roll-out to determine at what point we expect it to affect our study. The vaccinations are being rolled out by decreasing priority group and the government is aiming to vaccinate all patients who are aged 70 or over or CEV (priority group 4) by 15 February 2021. Although the window of ages around the threshold that we will use for this analysis will be determined through a data-driven approach, we anticipate that 5 years either side will likely be sufficient to create the window, so are expecting that we can use data collected until at least 15 February 2021 (subject to checks).

The PRINCIPLE trial is particularly problematic for this study, as the eligibility criteria are similar to CO@h: patients are enrolled if they are aged over 65, or aged over 50 and have certain underlying health conditions (which overlap but differ from the CEV list). These criteria imply there will be the same age-related discontinuity in patients enrolled on the PRINCIPLE trial as there is with CO@h. This will cause any findings from the current study to arguably comprise a mixture of effects of both PRINCIPLE and CO@h. To identify the potential for confounding, we will attempt to examine the likely overlap of patients between CO@h and PRINCIPLE.

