COVID-19 vaccinations commenced in December 2020, starting with older care home residents and care home staff, then moving down the priority list. By 15 February 2021, all patients aged 70 and over or CEV should have been offered a vaccination. If vaccinations are effective in stopping people getting COVID-19, this will affect the size of our cohorts, rather than confound our results. However, if vaccinated patients can still get COVID-19 but with milder symptoms (and therefore less likely to require hospital care), this could confound our analysis. We will be provided with information on the roll-out of the vaccinations and will aim to end the study period before or at the point vaccinations start being routinely provided to patients aged 65–70. This will ensure that there is limited confounding close to the threshold. The study period can be, if appropriate, tailored to different areas depending on local vaccination rates.

Some of the outcomes of this study may be difficult to interpret, either because of opposing mechanisms at play or because of other interventions, such as CVWs. However, our primary outcomes, relating to critical care and mortality, are expected to be easier to interpret. The qualitative analysis may also be able to provide contextual information to help interpret our results.

The aim of CVWs is to discharge patients earlier to alleviate the current pressures in hospitals. This could therefore impact on one of the outcomes of the CO@h evaluation: hospital bed days. As we will not have access to data on virtual ward enrolment, we are not able to assess whether CVWs affect patients' total hospital bed days in the CO@h intervention or control groups differently, and therefore whether any difference – or lack of difference – in outcomes is due to CO@h or CVWs. Although patients who are discharged early with CVWs may in general have different characteristics, eg in age, from those that are not, we do not expect a

discontinuity at age 65. Likewise, while CVWs may be used more in areas where there is the most pressure on hospital beds, by virtue of 'treated' and 'control' patients being found within the same areas and hospitals, we do not expect this to cause any bias in our analyses.

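### If the selected half-width exceeds about 2.5 years, the upper placebo threshold in sensitivity analysis 5 compares age groups with different vaccination priority, and its result cannot be interpreted

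*SAP*

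**What the plan says.** Sensitivity analyses, item 5, plans two placebo checks: "we will estimate treatment effects at both a lower and a higher threshold than age 65". Both are expected to show no effect. The lower one uses control patients only and the upper one treated-side patients only. Their position is fixed by "We will test at thresholds centred on the first mass point past the end boundaries of the window used in the main analysis", and their width by "We will use the same window size (ie number of mass points either side) as in the main analysis".

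The main half-width is not fixed in advance. The footnote under Sources of data says "The range or window of ages required will be determined using data-driven methods", and Window selection grows the window from 1 week: "The window will then be increased by 1 week either side of the threshold and the process repeated". The section on study period, index dates and follow-up nevertheless gives an expectation: "we anticipate that 5 years either side will likely be sufficient to create the window". On that basis it expects to use data to at least 15 February 2021, subject to checks.

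The Vaccinations section defines priority group 4 as "Individuals 70 years of age or over and CEV individuals"; ages 65 and over follow in group 5. Strengths and limitations adds: "By 15 February 2021, all patients aged 70 and over or CEV should have been offered a vaccination". It accepts that milder disease in vaccinated patients could confound the analysis. Its safeguard is to end the study period by the time people aged 65 to 70 are routinely vaccinated, which protects the neighbourhood of age 65. Nothing in the SAP addresses vaccination at the placebo thresholds.

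**The concern.** The SAP allows data to mid-February because a 5-year window leaves patients aged 70 or over outside the main comparison. Item 5 then brings them back as one side of a comparison that is supposed to be null. CEV patients, who share priority group 4, are excluded from the cohort, so age alone separates groups 4 and 5 among those analysed.

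Two misreadings become possible. A lower risk above the cut, produced by vaccination, could be taken as failure of a sound design. Alternatively, vaccination could offset a rise in risk with age, so that the check appears to pass although the age gradient it should reveal is present. This matters because item 6, the placebo study period, is run only if the intention-to-treat result is statistically significant. Item 5 may therefore be one of few outcome-based checks available.

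**Working it through.** **Inputs from the SAP.** Threshold 65; age in whole weeks; placebo cut one mass point beyond the main window; same number of mass points either side; anticipated half-width 5 years; vaccination boundary at age 70; roll-out start 8 December 2020; earliest study start about the beginning of December 2020; data to at least 15 February 2021.

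**Geometry.** With 365.25/7 = 52.18 weeks per year and a half-width of *k* weeks, upper cut = 65 + (*k* + 1)/52.18 and upper window = cut ± *k*/52.18. The lower placebo is the mirror image.

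| Half-width | Upper cut | Upper window | Share of age range above the cut that is 70+ |
|---|---|---|---|
| 2 years | 67.01 | 65.02–69.01 | 0% |
| 2.5 years | 67.51 | 65.02–70.00 | about 0% |
| 3 years | 68.03 | 65.02–71.04 | 34% |
| 4 years | 69.02 | 65.02–73.03 | 76% |
| 5 years | 70.02 | 65.02–75.02 | 100% |

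At 5 years only about 0.4% of the age range below the cut is 70 or over, so the two sides are almost exactly groups 4 and 5. The lower placebo at 5 years has its cut at 59.98 and a window of 54.98–64.98. None of those ages was due an age-based offer by mid-February.

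**Calendar.** From 1 December 2020 to 15 February 2021 is 76 days, of which the last 69 follow the start of vaccination. Groups 1 to 3 came before group 4, and the SAP does not say when people aged 70 to 74 began to be vaccinated.

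**Possible size (assumptions, not SAP figures).** The power formula was first checked against the SAP: pooled-variance two-proportion sample sizes reproduce all 21 cells of Table 1 (for example 21,590 at 2.0% baseline risk and relative risk 75%). At 11,000 per group, 2% against 1.5% gives 80.7% power, matching the SAP's figure of around 22,000 in total.

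Suppose 5–50% of index cases above the cut are vaccinated and protected, with 50–80% protection. Relative risk from vaccination alone = 1 − coverage × protection, which runs from 1 − 0.05 × 0.5 = 0.975 to 1 − 0.50 × 0.8 = 0.60. At 2% baseline risk and 22,000 patients, the chance of a significant result from vaccination alone is:

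- relative risk 0.975: about 5%, practically undetectable
- relative risk 0.75 (50% coverage, 50% protection): 81%
- relative risk 0.60: over 99%

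**Masking.** The two 5-year halves have mean ages about 5 years apart. With an assumed 3–10% rise in risk per year, the age-only relative risk is 1.03^5 = 1.16 to 1.10^5 = 1.61. It is cancelled when coverage × protection = 1 − 1/1.16 = 0.14 to 1 − 1/1.61 = 0.38, which lies inside the assumed range.

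**How likely is a wide window?** The stopping rule was simulated with no age trend, equal weekly counts and independent tests at p < 0.10. The chance of growing beyond 130 weeks is about 0.02% with nine tests, 0.8% with five and 6% with three. For reaching 260 weeks it is about 0.004%, 0.4% and 4%.

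**The case against.** The strongest reply is that the overlap may never arise. The 5-year figure is an expectation, and the binding rule stops before the first baseline difference at p < 0.10 across nine listed variables. The simulation suggests the window would rarely pass 2.5 years even without age trends, and the SAP expects trends in multimorbidity and diabetes; the power-based criterion can only narrow it. This stands, and it is why the point is conditional. The simulation rests on its own assumptions, however, and the SAP plans around 5 years without saying what happens to item 5 if that width is reached.

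A reader might infer that the upper check simply tests vaccination. The documents do not support that. Coverage at ages 70 to 74 was partial and is undated, and the study may end earlier: it must stop before any change of the age threshold, and an extension to ages 50 and over was recommended in early February 2021. The upper check would mix two influences.

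A reader might also infer that item 5 as a whole is void, or that the age-65 analysis is undermined. Neither follows. The lower placebo is clear of the boundary, the main window at 5 years stops at about 70, and other sensitivity analyses also examine the design.

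Finally, the SAP will monitor the roll-out, may tailor study periods by area and will record later decisions in an addendum. Those provisions are aimed at age 65 and give no rule for reading the upper placebo.

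**Conclusion.** The point holds conditionally. For half-widths up to about 2.5 years there is no problem. Above that, the upper placebo compares groups with different vaccination priority, and at the SAP's own anticipated 5 years it does so completely. In that case neither a non-zero nor a null upper result could be read as evidence about the age-65 design.

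The geometry follows from the SAP alone. The size of the distortion does not: under the assumed coverage and protection it ranges from undetectable to almost certain to be significant, and the SAP has no figures to narrow this. It also assumes that the study period runs into the time when the 70+ group was being vaccinated. The change is worth making because it is cheap and can be fixed before the data are seen.

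**What to change.** Add a conditional rule to item 5. If the selected main half-width exceeds about 2.5 years, restrict the upper placebo to ages 65 to under 70, with its cut at about 67.5 and its half-width capped at about 2.5 years whatever the main width. In whole weeks, 129 each side starting from 65.02 ends at 65.02 + 258/52.18 = 69.96. The cap must be absolute: half the main width would cross 65 and 70 once the main half-width exceeds 5 years.

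Alternatively, if area-level roll-out dates are obtained, restrict the upper placebo to index dates before vaccination of the 70+ group in that area. The SAP does not give these dates, and few weeks of data may remain.

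Under either option, re-run the baseline balance rule at the threshold used and state how a non-zero result will be read. Keep the lower placebo as planned.

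The cost is SAP wording, a further run of the placebo analysis and, for the calendar option, sourcing dates. The upper check also becomes smaller and less precise: if weekly counts were equal (assumed), going from 5 to 2.5 years halves the sample and widens the standard error by √2, about 1.4 times.
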